### Efficacy Endpoints

[figure not shown]
Tumor response and disease progression will be evaluated by the independent central review (ICR) for the Part 4 primary endpoint and the Part 3 secondary endpoint; and by the investigator for secondary efficacy endpoints (Parts 3 and 4) according to the Lugano Classification for Lymphoma ([Cheson, 2014](#)).

All subjects who receive at least 1 dose of study medication will be included in the full analysis set (FAS) for the efficacy analysis.

The efficacy analysis will include the ORR, DOR, and DCR at the Final Study Assessment Visit. Subjects who have not progressed at the time of analysis will be censored at the date of their last tumor assessment. Progression-free survival and OS will also be presented using Kaplan-Meier techniques.

The overall response rate (ORR) and DOR will be descriptively summarized; exact 95% confidence intervals (CI) will be produced.

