### 9.3.2.2 Secondary Efficacy Variables

The secondary efficacy variables will be PFS, DCR, DOR and OS. All secondary efficacy variables will be determined from the radiological tumor scans according to the Lugano Classification for Lymphoma ([Cheson, 2014](#)) relative to the FAS population.

Secondary efficacy variables will be evaluated separately for Parts 3 and 4.

The DCR will be defined as the percent of subjects with objective response of CR, PR, or SD, (defined as SD for 6 months or longer). The DCR will be analyzed using similar methods as the ORR.

For subjects who continue to receive treatment after radiographic PD, and have confirmed PD at next assessment, the time of PD will be that of the first detection.

The DOR will be defined as the time from the first documented objective response (CR or PR) to the date of PD or death from any cause. Subjects who have not progressed at the time of data base lock will be censored at the date of their last tumor assessment.

The PFS will be defined as the time from the start of treatment with MT-3724 on C1D1 to the date of PD or death from any cause. Subjects who have not progressed at the time of data base lock will be censored at the date of their last tumor assessment.

For both DOR and PFS, those subjects who have no data on progression (eg, subjects who discontinued the study due to other reasons than progression and who were not followed up until progression) and/or have no data on tumor assessment after baseline and are still alive will be censored at the subject's date of first dose.

The OS will be defined as the time from the start of treatment with MT-3724 until death from any cause.

The DOR, PFS and OS will be summarized descriptively using the Kaplan-Meier methods (K-M median and corresponding 95% CI, quartiles, number of events, number censored, Kaplan-Meier figure). Since these methods assume missing data are missing at random, supportive analyses will be conducted assuming data are missing not at random.

As a secondary sensitivity analysis for efficacy (eg, study drug exposure, lines of prior therapy, DOR to prior therapy, subject subsets), the mFAS population will be utilized. The same statistical techniques will be applied on each efficacy endpoint on the mFAS population.

Data listings will be created to support each analysis and to present all efficacy data.

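### Conflicting censoring rules for DOR and PFS: the first-dose rule erases observed PFS time and puts some DOR censoring dates before DOR starts

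*Protocol*

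**What the plan says.** Protocol Section 9.3.2.2 contains two rules.

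- **Last-assessment rule**, given once for DOR and once for PFS: "Subjects who have not progressed at the time of data base lock will be censored at the date of their last tumor assessment". The Synopsis, under Efficacy Endpoints, has the same rule: "Subjects who have not progressed at the time of analysis will be censored at the date of their last tumor assessment".
- **First-dose rule**, in a later paragraph. It opens with "For both DOR and PFS, those subjects who have no data on progression", and its example is "subjects who discontinued the study due to other reasons than progression and who were not followed up until progression". An and/or then joins a second condition, which carries the censoring date: "have no data on tumor assessment after baseline and are still alive will be censored at the subject's date of first dose".

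The time origins in the same section differ. For PFS: "The PFS will be defined as the time from the start of treatment with MT-3724 on C1D1". For DOR: "The DOR will be defined as the time from the first documented objective response (CR or PR) to the date of PD", with death also counted as an event.

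DOR is the key secondary endpoint of Part 4 (Protocol Section 3.2). The supplied SAP (Section 1.3.5.2) censors DOR and PFS at the last disease assessment and has no first-dose rule. It is based on protocol v7.0 (SAP Section 1.2) and does not cover Parts 3 and 4.

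**The concern.** The first-dose rule has two limbs: no data on progression, and no post-baseline tumor assessment. Because they are joined by and/or, the first is enough alone. The plan's own example of the first limb is a subject who left early without progression, and such a subject may have several clean scans. The last-assessment rule covers the same person and gives a different date.

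Under the first-dose rule, PFS follow-up that was actually observed counts as zero. For a responder the censoring date comes before the DOR clock starts. A programmer would then have to drop the responder, set the time to zero or improvise, possibly after seeing the data. Events stay in the analysis while event-free time is removed, so the Kaplan-Meier medians tend to fall, and the number at risk for DOR may not match the number of responders. In a single-arm trial, DOR is what gives the response rate its meaning.

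**Working it through.** **1. The plan's own figure.** The only operating characteristic stated is for the Part 4 ORR rule: at least 23 of 88 responders, 17% against 32%, power 90.4%, one-sided alpha below 0.025 (Protocol Section 4.1.2). Exact binomial:

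- P(X ≥ 23 | n = 88, p = 0.17) = 0.0201
- P(X ≥ 23 | n = 88, p = 0.32) = 0.9039

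This reproduces, and it uses no censoring date.

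**2. Dates under each rule.** Scans are every 6 weeks (± 1 week) from C1D1 (Protocol Table 1-1), so a response at the first scheduled scan falls at about week 5 to 7.

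- PFS under the first-dose rule = first dose − C1D1 = 0
- DOR under the first-dose rule = first dose − date of response = −(time to response)

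| Living subject, no PD | PFS, first dose | PFS, last scan | DOR, first dose | DOR, last scan |
|---|---|---|---|---|
| Response week 6, last scan week 24 | 0 | 24 wk | −6 wk | 24 − 6 = 18 wk |
| Response week 12, last scan week 36 | 0 | 36 wk | −12 wk | 36 − 12 = 24 wk |
| Response and last scan week 5 | 0 | 5 wk | −5 wk | 0 |
| Response and last scan week 7 | 0 | 7 wk | −7 wk | 0 |

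**3. Which limb does the damage.** A living subject with no post-baseline scan has no PFS time to lose, so C1D1 is the conventional date. Every responder has a post-baseline scan, so the second limb can never apply to DOR. The whole defect sits in the first limb, and for DOR the first-dose date is never valid.

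**4. Illustrative size.** The documents give no median DOR, median PFS or drop-out rate, so everything here is assumed: exponential event times, 6 to 24 months of follow-up, 1,500 replicates, and 0.32 × 88 ≈ 28 responders. Correct censoring is compared with the first-dose rule, under which an affected subject contributes no time at risk.

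| Endpoint | Assumed true median | Share affected | Median, correct censoring | Median, first-dose rule |
|---|---|---|---|---|
| DOR, 28 responders | 6 months | about 6% to 23% | about 6.0 | 5.7 down to 4.6 |
| PFS, 88 subjects | 3 months | about 5% to 22% | about 3.0 | 2.8 down to 2.4 |

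At about 11% affected, the DOR median goes from about 6.0 to 5.3 months and the PFS median from about 3.0 to 2.7.

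**5. Second model.** Here events are detected only at 6-weekly scans, follow-up is capped at 18 months, and 10% to 40% stop without PD. With a true median of 6 months (88 subjects for PFS, 23 responders for DOR), last-scan censoring gives about 6.9 months; the excess over 6 arises because PD is dated at the next scan. First-dose censoring gives 5.5 down to 4.1 months and discards about 6% to 30% of person-time. With a true median PFS of 2 months and 10% to 30% stopping, the median did not move. No scenario moved it upward.

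**6. Hand check.** For exponential times the median is ln 2 × person-time / events, so losing a fraction f of person-time multiplies it by 1 − f: 6.0 × (1 − 0.06) = 5.6 and 6.0 × (1 − 0.30) = 4.2 months, the same order as the simulations.

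**The case against.** The strongest reply is that the intended rule is clear and few subjects are caught. Last-assessment censoring appears twice in Section 9.3.2.2 and once in the Synopsis, and the SAP for earlier parts agrees. The protocol leaves detailed methods to a Parts 3 and 4 SAP that may modify its plans (Section 9). That SAP is not among the documents, so nobody can show that a negative DOR would be programmed. DOR and PFS are descriptive, the bias runs against the drug, and no data are lost. With 28 responders, the correctly censored median itself ranged from about 3.4 to 10.4 months between replicates, far wider than the shift.

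All of this stands and limits the severity. It does not remove the conflict, because the first-dose paragraph explicitly covers both endpoints and its example is a subject the last-assessment rule also covers. The missing-not-at-random analyses promised in the same section do not change the censoring date.

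A reader might infer more than the documents support:

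- *All responders get a negative DOR.* Only living responders who leave without PD and are not followed to PD do.
- *Stopping for toxicity triggers the rule.* It does not by itself. Such subjects stay in PFS follow-up (Synopsis, Long-Term Follow-up; Section 9.3.1), and those with CR, PR or SD have imaging until PD, death or new anticancer treatment (Section 8.1.5). Withdrawal, loss to follow-up and new therapy can trigger it.
- *Everyone without PD at database lock is censored at first dose.* That would cancel the explicit last-assessment rule and ignore the example.
- *The DOR date is always at least 5 weeks too early.* Section 8.3.1 allows unscheduled scans, so a response may be documented sooner.

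**Conclusion.** Wrong as written; should-fix. For living subjects who leave without progression and are not followed to it, Section 9.3.2.2 prescribes two different censoring dates. The first-dose date discards their observed PFS time and is impossible for DOR.

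The date conflict and the negative DOR follow from the text and the scan schedule alone. The size in months does not: it rests on assumed medians, drop-out and follow-up. Under those assumptions the DOR median falls by about 0.3 to 1.4 months (6.0 − 5.7; 6.0 − 4.6) and the PFS median by about 0.2 to 0.6 months (3.0 − 2.8; 3.0 − 2.4). Downward bias is a tendency, since some short-median cases showed no shift.

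The Part 4 conclusion rests on ORR and does not change. The point matters because DOR is the key secondary endpoint and is read from a small number of responders.

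**What to change.** Replace the first-dose paragraph in Protocol Section 9.3.2.2 with:

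> Subjects without PD or death are censored at the last evaluable tumor assessment. For PFS only, living subjects with no post-baseline tumor assessment are censored at C1D1. For DOR, responders with no later assessment are censored at the date of first response (1 day).

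Carry the same rule into the SAP for Parts 3 and 4 before database lock. The cost is one paragraph. It needs no new data, adds no burden on subjects and leaves the sample size and the ORR decision rule as they are.

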##### **6.1.1.3 Dose Schedule**

All doses of MT-3724 will be administered as IV infusion over 1 hour (window = 54 to 75 minutes) in a 21-day cycle according to the schedule specified in each cohort ([Table 6-1](#)).

NOTE: Each dose of MT-3724 must be preceded by premedication administered within 60 minutes before the start of each infusion (see [Section 6.1.2](#))

All doses should be administered within the first 16 days of the 21-day cycle. For Cycle 1 and 2 doses are preferably administered on Days 1, 3, 5, 8, 10, and 12 ( $\pm 1$  d). For Cycle 3 and later doses are preferably administered on Days 1, 8, and 15. All cycles should use the following guidelines:

- The first 3 doses of Cycle 1 must be administered at least 2 days (approximately 48 hours) apart.
- All subsequent doses must be at least 20 hours apart (more than 5 half-lives of MT-3724 in serum), and must not be administered on more than 2 consecutive days.

The first dose of the first cycle will require approximately 5 hours in the clinic which include approximately 4 hours of post-dose safety assessments. Subsequent doses will require approximately 3 hours in the clinic which include approximately 2 hours of safety assessments post-dose (see also [Section 1.3, Schedule of Activities \(SoA\)](#)).

No more than 14 days should elapse between cycles. If more than 14 days elapse, the investigator must consult with the medical monitor before initiating the next cycle of treatment. Refer to [Section 6.2](#) for dose modification guidelines and management of toxicities.

Treatment will continue until death, disease progression, unacceptable toxicity, withdrawal of consent, or another reason for withdrawal, or until study discontinuation.

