#### **6.1.1.4 Treatment Beyond Progression**

For subjects who have radiological, but not clinical, evidence of disease progression within 3 months of C1D1, in lieu of discontinuation, the investigator may continue treatment at the dose they are given at the time progression is identified if s/he believes the benefit outweighs the risk and provided the conditions identified below are met.

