## 9.2 Populations for Analyses

For purposes of analysis, the following populations are defined:

Population	Description
Full analysis set (FAS) population	All subjects who received at least 1 dose of MT-3724 monotherapy treatment. This will be the primary population for the assessment of efficacy endpoints.
Modified full analysis set (mFAS) population	All subjects who have at least 1 post-baseline efficacy assessment; subjects without a post-baseline efficacy assessment will not be considered evaluable for the primary efficacy analysis. Subjects who discontinue due to disease progression or die, prior to disease assessment will be included.
PK analysis population	All subjects who received any amount of MT-3724 and for whom the on-treatment PK data are considered to be sufficient and interpretable.
Immunogenicity analysis population	All subjects who have received any amount of MT-3724 and have valid post-baseline immunogenicity assessment will be included in the analysis set for the immunogenicity analysis.
Pharmacodynamic analysis population	All subjects who have received any amount of MT-3724 and have at least 1 valid post-baseline pharmacodynamic assessment.
Safety analysis population	All subjects who received at least 1 dose of MT-3724 monotherapy treatment. For this study, this is equivalent to the FAS population.

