4.5. Study Drug Exposure

Study drug exposure analyses will be conducted using the Safety Set.

All study drug exposure analysis will also be performed by subgroup as defined in Section 3.8.

Study drug exposure will be calculated as the number of days subjects were administered study drug, as determined below, and will be summarized by treatment group using descriptive statistics.

$$\begin{aligned} \text{Duration of Study Drug Exposure (days)} \\ = (\text{Date of last infusion} - \text{Date of first infusion}) + 1 \end{aligned}$$

The number of dosing cycles completed will be tabulated for each treatment group.

Total drug received (both in mcg and mcg/kg), dose intensity (defined as total drug received divided by duration of exposure), number of doses taken, number of missed doses, number of dose interruptions, duration of dose interruption, and number of dose reductions will also be summarized.

Dosing information for each subject will be presented in a data listing by treatment group.

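### Efficacy by study drug exposure is planned with exposure undefined for Parts 3 and 4 and no landmark; if exposure means time on drug or total dose, treatment until progression builds in an apparent benefit

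*Protocol*

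**What the plan says.** Protocol Section 9.3.2.2, on the mFAS: "As a secondary sensitivity analysis for efficacy (eg, study drug exposure, lines of prior therapy, DOR to prior therapy, subject subsets), the mFAS population" is to be used, and "The same statistical techniques will be applied on each efficacy endpoint on the mFAS population". For this trial those techniques are exact proportions and Kaplan-Meier summaries.

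On how long subjects are treated, Section 6.1.1.3 says "Treatment will continue until death, disease progression, unacceptable toxicity, withdrawal of consent, or another reason for withdrawal, or until study discontinuation". There is no limit on cycles. Section 6.1.1.4 allows an exception for radiological, non-clinical progression within 3 months of C1D1, when "the investigator may continue treatment at the dose they are given at the time progression is identified".

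On the endpoints, Section 9.3.2.2 says "The PFS will be defined as the time from the start of treatment with MT-3724 on C1D1 to the date of PD" or death, so PFS starts on the day exposure starts. DCR counts stable disease only if it is "SD for 6 months or longer".

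No section defines exposure for Parts 3 and 4. SAP Section 4.5 says "Study drug exposure will be calculated as the number of days subjects were administered study drug, as determined below"; its formula is last infusion date minus first infusion date plus 1. It also lists total drug received, number of doses and dose intensity. That SAP is based on protocol v7.0 and covers Parts 1 and 2.

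Protocol Section 9.2 makes the FAS the primary efficacy population. The mFAS is "All subjects who have at least 1 post-baseline efficacy assessment", plus subjects who discontinued for progression or died before an assessment.

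**The concern.** Days on drug, number of doses and cumulative dose all accumulate only while a subject is still being treated, and progression normally ends treatment. Grouping subjects by such a measure therefore groups them partly by outcome: the long-exposure group had to remain progression-free to get there. This is immortal-time, or guarantee-time, bias.

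ORR is affected too. A subject who progresses before the first 6-weekly scan stops drug early and is not a responder, so low exposure and non-response share a cause. DCR is affected because 6 months without progression is part of its definition.

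What is at stake is interpretation. A table of PFS, DCR or ORR by exposure could be read as an exposure-response signal when the stopping rule alone produces the pattern. The planned techniques contain nothing to remove it.

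**Working it through.** **1. The plan's own figure.** The documents give no figure for the exposure analysis. The one figure that can be reproduced is for the Part 4 rule (Section 9.1). With X ~ Binomial(88, p):
- alpha = P(X ≥ 23 | p = 0.17) = 0.0201, below 0.025
- power = P(X ≥ 23 | p = 0.32) = 0.9039, matching the stated 90.4%

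This confirms the design size used below. Nothing in the exposure analysis enters this rule.

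**2. Simulation with no effect of exposure.**

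From the protocol: n = 88; scans every 6 weeks (42/30.44 = 1.38 months); drug stops at detected progression; PFS starts at C1D1.

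Assumed, not in the documents:
- exponential PFS with median 2, 3, 4 or 6 months
- a hazard of stopping drug for other reasons of 0, 0.05, 0.1 or 0.2 per month, unrelated to progression, with progression still observed afterwards
- a 35% chance of response if progression-free at the first scan
- follow-up cut at 18 months from C1D1

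Each setting had 1,000 trials. Subjects were split at median days on drug and compared on PFS by log-rank at nominal two-sided 5%. Entries are the percentage of trials with a nominally significant difference, with the median hazard ratio, long versus short exposure, in parentheses.

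| Median PFS (months) | Stop hazard 0 | 0.05 | 0.1 | 0.2 |
|---|---|---|---|---|
| 2 | 100% (0.06) | 100% (0.15) | 99.8% (0.23) | 99.3% (0.33) |
| 3 | 100% (0.05) | 100% (0.17) | 99.7% (0.28) | 89.2% (0.46) |
| 4 | 100% (0.04) | 100% (0.21) | 99.4% (0.33) | 74.1% (0.55) |
| 6 | 100% (0.04) | 100% (0.24) | 95.8% (0.40) | 58.7% (0.59) |

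The true hazard ratio for exposure is 1 in every cell. Other endpoints at median PFS 4 months, long versus short exposure:
- stop hazard 0: median PFS 9.4 vs 2.7 months; progression-free at 6 months 87% vs 0.2%; ORR 35% vs 21%
- stop hazard 0.2: median PFS 6.4 vs 2.9 months; progression-free at 6 months 51% vs 27%; ORR 35% vs 21%

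**3. Controls** (median PFS 2, 4 and 6 months).
- Grouping by a measure unrelated to time on study, stop hazard 0.05: 4.8% to 5.6% of trials significant, hazard ratio 1.0.
- Subjects progression-free at 12 weeks, grouped by exposure up to 12 weeks, stop hazard 0.1: 5.2% to 6.7%, hazard ratio 0.98 to 0.99. The unadjusted split at the same hazard and medians gives 95.8% to 99.8%.

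The test is two-sided, so the control percentages count differences in either direction.

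**4. Subjects lost to a Day 21 landmark.** With exponential PFS of median m months and progression seen as it happens, the share progressing by Day 21 (0.69 months) is 1 − 2^(−0.69/m):
- m = 4: 11%, about 10 of 88
- m = 2: 21%, about 19 of 88

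The first scheduled scan is at about week 6, so fewer would be recorded as progressed by Day 21.

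**The case against.** The strongest reply is that the plan never specifies a split by time on drug. The sentence is a loose list of examples, the following sentence ties the techniques to the mFAS rather than to exposure groups, and exposure could mean PK exposure or dose intensity. Section 9 leaves detailed methods for Parts 3 and 4 to a SAP, and Section 9.3.4.2 sends exposure-response modeling to a separate plan; neither is among the documents. This stands to the extent that the problem is conditional on the measure chosen. It does not remove the point: the text permits the biased version and names no safe one.

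Dose intensity is not automatically safe. Applying the SAP formula to full Cohort 2 dosing in Table 6-1 gives 170/12 = 14.2 µg/kg/day after one cycle, 470/33 = 14.2 after two and 1070/120 = 8.9 after six, so it also changes with time on treatment.

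A reader might infer four stronger things that the documents do not support:
- **That exposure is virtually PFS.** Stops for toxicity or withdrawal, and treatment beyond progression, loosen the link. They weaken the bias without removing it.
- **That anyone who stops before week 6 cannot be a responder.** The Schedule of Activities continues scans until progression, death or loss to follow-up, and Section 8.1.5 continues imaging for subjects with CR, PR or SD. Early stoppers can still respond; the simulation allows this.
- **That the tables would drive the choice of regimen.** Section 6.1.1.2 bases that on DLTs in Part 3, before Part 4 begins.
- **That the mFAS discards early failures.** Its definition keeps subjects who discontinued for progression or died before assessment.

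The analysis is also descriptive: Section 9 states that the design has no inferential methods.

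**Conclusion.** The concern holds conditionally. If exposure is days on drug, number of doses or cumulative dose, the planned summaries of PFS, DCR and ORR by exposure will favor longer exposure whether or not exposure matters. The direction was the same in all 16 settings. The size, 59% to 100% of trials with a nominally significant PFS difference and median hazard ratios of 0.04 to 0.59, rests on the assumed PFS distribution, stopping hazards and response chance, and on a median split that the protocol does not itself specify. OS and DOR were not simulated.

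The primary test and the regimen choice are untouched. The consequence is confined to how the secondary exposure tables are read, but the correction is simple and should be made.

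A smaller related point also stands. The same sentence puts the baseline subgroups (prior lines, DOR to prior therapy) on the mFAS, which still drops subjects with no post-baseline assessment who left for reasons other than progression or death.

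**What to change.** In Section 9.3.2.2, and in the SAP for Parts 3 and 4, do one of the following:
- Define exposure over a fixed early window, for example the share of the planned Cycle 1 dose received by Day 21. Analyze outcomes from a landmark at the end of that window among subjects alive and progression-free then, and report how many the landmark excludes.
- Delete study drug exposure from the list.

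Run the baseline subgroups on the FAS first, with the mFAS as a repeat.

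The cost is wording, with no new data or subjects. The landmark removes up to about 11% to 21% of subjects at median PFS of 4 to 2 months if progression were seen continuously, and fewer with 6-weekly scans. The simulated landmark was at week 12; a Day 21 landmark follows the same logic but was not simulated. A landmark removes the time bias only: subjects in worse condition may still receive less drug early, so the tables should be labeled descriptive.

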#### **4.1.2      Part 4**

The goal of Part 4 is to provide sufficient evidence to test the null hypothesis that the true response rate with MT-3724  $\leq$  17% vs the alternative hypothesis that the true response rate with MT-3724  $\geq$  32% at the 1-sided alpha level of 0.025 with high statistical power. At least 88 evaluable subjects will be required to test the null hypothesis vs the alternative hypothesis in Part 4. If at least 23 of 88 subjects respond at the end of Part 4, then the null hypothesis is rejected in favor of the alternative hypothesis and the effectiveness of MT-3724 as monotherapy will have been proven. Under the stated null and alternative hypotheses, Part 4 carries 90.4% power at the 1-sided alpha level of < 0.025.

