**Table 6-4. MT-3724 Dose Modification Guidance and Specific Management of Toxicities**

	Specific Management	MT-3724 Dose Modificationa

Grade <math>\geq</math> 2 CLS: As defined in CTCAE v5.0, or if at least 2 of the following within the same cycle (unless unequivocally related to underlying condition) reaches the level of Grade 2:
 
 
• Hypoalbuminemia
 
• Hypotension
 
• Edema (peripheral or central, all types) and/or weight gain
 
	
Subjects should be closely monitored for signs of CLS. This includes:
 
 
• Monitoring of vital signs (temperature, heart rate, BP, respiration rate), body weight, edema of any type including both peripheral edema and central edema (such as pleural effusion or signs of dyspnea).
 
• Monitoring of laboratory parameters including hemoconcentration (eg, hematocrit, Hb), and especially albumin and CK in case of clinical symptoms indicative of CLS.
 
 
Investigators should consider supportive measures while on trial regardless of dosing or timing of dosing. If a subject experiences Grade 2 hypotension, orthostasis, edema, or hypoalbuminemia, normal saline and/or an albumin infusion may be given, as needed.
	
Treatment modification due to CLS:
 
 
• For Grade <math>\geq</math> 3 CLS, the MT-3724 treatment must be permanently discontinued.
 
• For Grade 2 CLS, the MT-3724 treatment must be held, and may only be restarted after: 
 
◦ a minimum of 7 days has elapsed after onset of CLS, and
 
◦ all signs and symptoms of CLS have resolved to at least grade 1, and
 
◦ albumin has remained <math>\geq</math> 3.0 g/dL for at least 5 days post last albumin infusion (if required) without additional albumin substitution
 
 
 
 
Subsequent doses of MT-3724 must be:
 
 
• reduced by at least 25%, and
 
• administered once weekly
 
 
or subject may be permanently discontinued at the investigator's discretion.

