### 9.1 Statistical Hypothesis and Sample Size Determination

In Part 3, approximately 25 subjects will be enrolled as a continuation of the expansion of the MTD cohort with the intention to verify the safety, dose and dosing schedule (completion of the Phase 1b).

In Part 4, approximately 88 evaluable subjects will be enrolled. If at least 23 of 88 evaluable subjects respond at the end of Part 4, then the null hypothesis is rejected in favor of the alternative hypothesis and the effectiveness of MT-3724 as monotherapy will have been proven. Under the stated null and alternative hypotheses, Part 4 carries 90.4% power at the 1-sided alpha level of < 0.025.

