### **9.3.2.1        Primary Efficacy Variable (for Part 4)**

The primary efficacy variable is the ORR. The ORR is defined as the percent of subjects with CR or PR determined by the blinded, ICR according to the Lugano Classification for Lymphoma ([Cheson, 2014](#)), relative to the FAS population.

Overall response rate will be summarized by number and percentage of subjects meeting the definition of ORR along with the corresponding 2-sided 95% binomial exact confidence intervals (CI), separately for Parts 3 and 4.

In Part 4, with  $n = 88$  subjects, if  $\geq 23$  ORRs are seen, the null hypothesis is rejected in favor of the alternative hypothesis and the effectiveness of MT-3724 as monotherapy will have been proven.

Subjects with missing disease assessments such that objective response cannot be determined will be assumed to be non-responders in the analysis.

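### The planned efficacy subset analyses are assigned to the mFAS, which omits only FAS non-responders, so subset ORR and DCR can only equal or exceed the FAS values and do not reconcile with the primary result

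*Protocol*

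**What the plan says.** Protocol 9.2 defines the FAS as all subjects given at least one dose and makes it the primary efficacy population. Section 9.3.2.1 measures ORR against the FAS and fixes the handling of missing response: "Subjects with missing disease assessments such that objective response cannot be determined will be assumed to be non-responders in the analysis". Section 9.3.2.2 analyses DCR by similar methods.

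The mFAS in 9.2 requires at least one post-baseline efficacy assessment, with one exception: "Subjects who discontinue due to disease progression or die, prior to disease assessment will be included".

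Section 9.3.2.2 then places the secondary sensitivity analysis on that set. Its examples are study drug exposure and "lines of prior therapy, DOR to prior therapy, subject subsets), the mFAS population will be utilized". The same techniques are to be applied to every efficacy endpoint. No other passage plans efficacy subset analyses, and none is assigned to the FAS. The missing-not-at-random analyses in the same section are tied to the Kaplan-Meier endpoints (DOR, PFS, OS), not to ORR or DCR.

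The supplied SAP does not change this. Its section 1.2 bases it on protocol version 7.0 and Parts 1 and 2, and its section 2.1 defines no mFAS.

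**The concern.** A subset analysis should break the primary result into parts that add back to it. Here the primary result is on all dosed subjects, while the subsets are on a set from which some non-responders have been taken out. The subset numerators add to the FAS numerator, but the denominators do not add to the FAS denominator. The rates are shifted in one direction only. If early exits without a scan are more common in one subset (for example, more heavily pretreated subjects), the shift differs between subsets and can suggest a difference that the FAS does not show.

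At stake is interpretation, not the formal decision. In a single-arm trial with a narrow margin around the cut-off, a borderline FAS result would be reported beside supportive and subset rates that cannot be lower, and nothing in the plan tells the reader so.

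**Working it through.** **Inputs.** From Protocol 4.1.2 and 9.1: null rate 17%, alternative 32%, n = 88, success rule "If at least 23 of 88 subjects respond at the end of Part 4". From 9.3.2.1: two-sided 95% exact binomial interval. The number k of FAS subjects missing from the mFAS is not in the documents. It is assumed here, with 5%, 10% and 15% of 88 as the main range.

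**1. The plan's own figure.** The protocol states that "Part 4 carries 90.4% power at the 1-sided alpha level of < 0.025". Exact binomial tails give:
- P(X ≥ 23 | 88, 0.17) = 0.0201
- P(X ≥ 23 | 88, 0.32) = 0.9039
- P(X ≥ 22 | 88, 0.17) = 0.0364

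The stated power and alpha reproduce, and 23 is the smallest valid cut-off.

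**2. Who is in which set.**

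| Dosed subject | FAS | mFAS |
|---|---|---|
| Has a post-baseline efficacy assessment | in | in |
| None; discontinued for progression, or died first | in, non-responder | in, non-responder |
| None; alive, left for another reason (toxicity, withdrawal, loss to follow-up) | in, non-responder | out |

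Only the last row differs.

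**3. Direction.** With x responders and k removed, ORR moves from x/88 to x/(88 − k), which is never smaller. The same holds for DCR, since a subject never assessed cannot be shown to have CR, PR or six months of SD. Within a subset of size n the rate is multiplied by n/(n − k). For 5%, 10% and 15% removed the factor is 1/0.95 = 1.05, 1/0.90 = 1.11 and 1/0.85 = 1.18. Two subsets that both have an FAS ORR of 25%, with 5% removed from one and 15% from the other, would show 0.25/0.95 = 26.3% and 0.25/0.85 = 29.4%.

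**4. Size at the boundary.** The Clopper-Pearson lower limit is the 2.5% quantile of Beta(x, n − x + 1).

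| FAS result | FAS lower limit | Smallest k that lifts the limit above 17% | mFAS result | mFAS lower limit |
|---|---|---|---|---|
| 22/88 = 25.0% | 16.4% | 4 | 22/84 = 26.2% | 17.2% |
| 21/88 = 23.9% | 15.4% | 8 | 21/80 = 26.3% | 17.04% |
| 20/88 = 22.7% | 14.5% | 13 | 20/75 = 26.7% | 17.1% |

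With three removed, 22/85 has a lower limit of 16.99%. Removing one to three subjects therefore does not lift 22 responders past 17%.

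**5. How often.** Let each dosed subject respond with probability p = 0.17 and, separately, be a removed non-responder with probability d. Given k removed, responders follow Binomial(88 − k, p/(1 − d)). Averaging over k ~ Binomial(88, d), with the smallest count whose exact lower limit exceeds 17% at each n = 88 − k:

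| Assumed d | P(FAS ≥ 23/88) | P(mFAS lower limit > 17%) | mFAS true rate, 0.17/(1 − d) |
|---|---|---|---|
| 5% | 2.0% | 3.1% | 17.9% |
| 10% | 2.0% | 5.3% | 18.9% |
| 15% | 2.0% | 8.3% | 20.0% |

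Fixing the number removed at exactly 4, 9 or 13 gives 3.6%, 6.0% and 9.8%. That is a different model of the same effect.

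**6. Other endpoints.** DOR uses responders only, so removal does not touch it. Under 9.3.2.2, living subjects with no post-baseline tumor assessment are censored for PFS at first dose, so removing them has little effect. OS could move either way, but it has its own FAS and missing-not-at-random analyses.

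**The case against.** **Stopping drug is not stopping assessment.** A reader might infer that every subject taken off treatment for toxicity in Cycle 1 vanishes from the supportive results. The documents do not support that. For Grade 3 or higher CLS, Table 6-4 says "CLS, the MT-3724 treatment must be permanently discontinued", which concerns dosing and not imaging. The Schedule of Activities has scans every six weeks from C1D1 that do not end with treatment, and 9.3.1 keeps subjects who leave for reasons other than progression in follow-up for PFS and OS. Anyone scanned later is in the mFAS, and toxic deaths are in it too. The removed group is only those never scanned, and may be small. This stands.

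**One direction is not itself a defect.** Counting undeterminable response as failure among all dosed subjects is already the worst case for missing response. Any other rule can only match or raise ORR, and an evaluable-set analysis legitimately shows what the conservative rule costs. This stands for the overall mFAS analysis. It does not justify using that set for the subsets.

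**No success rule exists for the mFAS.** A reader might infer that the mFAS could formally rescue a failed trial. It could not. The only decision rule is 23 of 88, the FAS is named primary, and 9.3.2.2 labels the mFAS analysis a secondary sensitivity analysis. The comparison with 17% above is illustrative, and in those scenarios the mFAS rate truly is above 17%. (The mFAS row of 9.2 also calls unassessed subjects not evaluable for the primary analysis. That wording needs reconciling with the FAS, but it is a separate matter.)

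**The subset assignment sits in a parenthesis of examples.** The text does not say that FAS subsets will be omitted, and a later SAP could add them. That is possible, but the current text names only the mFAS.

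**Conclusion.** The point holds as a limited one. As written, the subset and sensitivity analyses of ORR and DCR use a set that differs from the FAS only by the absence of certain non-responders. Their rates cannot fall below the FAS rates for the same subjects, and the subsets do not reconcile with the primary result. That follows from the definitions and needs no assumption.

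The size does rest on assumptions. With up to three subjects removed, 22 responders still give a lower limit below 17%; with four it is above. At assumed removal of 5% to 15%, the chance of an mFAS lower limit above 17% when the true all-treated ORR is 17% is 3.1% to 8.3%, against 2.0% for the FAS. The actual number removed could be lower than any of these.

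The formal Part 4 test, its alpha and its power are unaffected. DOR, PFS and OS are little affected or have other planned analyses. Redefining the mFAS to retain toxicity withdrawals would be a matter of preference and is not needed. This is a cheap improvement, not a flaw in the primary analysis.

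**What to change.** In Protocol 9.3.2.2, and in the SAP that covers Parts 3 and 4:

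- Run the analyses of ORR and DCR by lines of prior therapy, by DOR to prior therapy and in other subject subsets on the FAS, with missing response counted as non-response (for DCR, as disease not controlled).
- Keep the mFAS as a supportive overall analysis only. Show it beside the FAS result, with the number of excluded subjects and the reason for each exclusion.
- State that mFAS ORR and DCR cannot be lower than the FAS values, and that the mFAS result cannot support an efficacy claim if the FAS test fails.

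The cost is a few sentences. No new data, sample size change or procedure is needed. The downside is that subset rates become slightly less favourable than they would be on the mFAS.
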